### **8.3.2.17 Percentage of seizure-free days during the 12-week Maintenance Period and the 16-week Treatment Period**

The percentage of seizure-free days during the Maintenance Period and Treatment Period will be summarized using descriptive statistics. The change in the percentage of seizure-free days from the Baseline Period to the Maintenance Period and Treatment Period will also be summarized.

The percentage of seizure-free days during the 12-week Maintenance Period and during the 16-week Treatment Period will each be analyzed using ANCOVA with treatment group as the main factor, Baseline percentage of seizure-free days as a continuous covariate, and the categorical factors Region (Europe or Non-Europe) and Baseline SV2A use (Yes or No). The 95% CI will be presented for estimates.

### **8.3.2.18 Cumulative responder rate during the 16-week Treatment Period**

Cumulative responder rate curve will be generated by treatment group for the observable focal-onset seizures. The percent reduction in seizure frequency ranging from -25% to 100% will be shown on the X-axis and the percentage of responders experiencing at least the particular percent reduction will be shown on the Y-axis.

### **8.3.2.19 Change in the SSG score**

The numbers and percentages of subjects in each severity category will be summarized descriptively for Baseline and at each scheduled assessment visit along with the numbers and percentages of subjects in each of the 7 categories of change (much better through much worse). Summary will be provided for Visit 2, Visit 4, Visit 7, and the Last Visit during the Treatment Period. All data will be listed by subject.

### **8.3.2.20 Change in the QOLIE-31-P score**

The scoring algorithm for QOLIE-31-P is described in Section 8.3.1.3. Observed values and change from Baseline for QOLIE-31-P total score and subscale scores for Seizure Worry, Daily Activities/Social Function, Energy/Fatigue, Emotional Well-Being, Cognitive Function, Medication Effects, Overall Quality of Life, Health Status will be summarized descriptively for Visit 2, Visit 4, Visit 7, and the Last Visit during the Treatment Period. All data will be listed by subject.

### **8.3.2.21 Change in Hospital Anxiety and Depression Scale (HADS) score**

The HADS observed scores and changes from Baseline for depression and anxiety will be summarized descriptively for Visit 2, Visit 4, Visit 7, and the Last Visit during the Treatment Period. All data will be listed by subject.

### **8.3.2.22 Time to return to the Baseline 28-day adjusted observable focal-onset seizure count**

Time to return to the Baseline 28-day adjusted observable focal-onset seizure count during the 12-week Maintenance Period will be evaluated using Kaplan-Meier methods (French et al, 2015). The event date is the earliest date when the total number of seizures since the start of the Maintenance Period is equal or greater than the Baseline 28-day adjusted seizure count (ie, Baseline seizure frequency per 28-days described in Section 3.3.1). The time to event in days will be calculated as (the event date – start date of the Maintenance Period + 1). If the time to event is more than 28 days for a subject, it would indicate that during the Maintenance Period, it takes longer time for the subject to experience as many seizures as during the Baseline Period in 28 days, which is the result of reduced seizure frequency during the Maintenance Period. If the total number of seizures during the Maintenance Period is less than the Baseline 28-day adjusted seizure count, the subject will be censored as of the last day with non-missing seizure data during the Maintenance Period. Subjects who discontinued during the Titration and Stabilization Period will be censored as of Day 1. The median time to event and the associated 95% CI will be estimated using Kaplan-Meier methods. The log-rank test will be used to compare differences between each PSL dose group and placebo. The KM curves will be presented by treatment group.

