## **3.3 Definition of Baseline values**

### **3.3.1 Baseline for variables based on seizure count**

Baseline values for seizure frequency variables will be derived from diary data recorded by the subject during the 4-week Baseline Period. This diary is collected at the Baseline Visit (Visit 2, Day 1). The Baseline value will be the seizure frequency per 28 days during the Baseline Period and is defined as the number of seizures standardized to a 28-day baseline period. It is computed for each subject as the number of seizures recorded over the subject's baseline diary period, divided by the subject's total number of non-missing days in that period, multiplied by 28. See details for calculation of seizure frequency in Section 8.1.1.1.

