#### 4.2.1.1 Missing data caused by missing seizure diary

Seizure frequency will be computed over non-missing diary days. Diary compliance evaluation is described in Section 7.2. Subjects with diary data deemed unacceptably incomplete (during blinded data review) for the primary efficacy variable will be excluded from the PPS. If seizure type is known but the number of seizures is unknown, the number of seizures will be imputed using the median for the same seizure type (daily seizure number > 0) during the same analysis period (baseline or treatment period). Otherwise, the missing seizure number will be imputed using the count of next higher level of seizure type.

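### Time to the Baseline seizure count runs on calendar days with no rule for missing diary days, so a time over 28 days need not mean fewer seizures

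*SAP*

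**What the plan says.** SAP 8.3.2.22 places the event on the "earliest date when the total number of seizures since the start of the Maintenance Period is equal or greater" than the Baseline 28-day adjusted count. Time to event is "the event date – start date of the Maintenance Period + 1", which is elapsed calendar time. The section then interprets the result: "If the time to event is more than 28 days for a subject, it would indicate" that the subject took longer to accumulate the Baseline number of seizures, "which is the result of reduced seizure frequency during the Maintenance Period". For a subject who never reaches the target, "the subject will be censored as of the last day with non-missing seizure data during the Maintenance Period". Each padsevonil dose is compared with placebo by log-rank test.

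The target comes from SAP 3.3.1: seizures recorded in the Baseline diary, divided by the subject's "total number of non-missing days in that period, multiplied by 28".

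SAP 4.2.1.1 gives the general rules for missing diary data. "Seizure frequency will be computed over non-missing diary days". There is also a count imputation: "If seizure type is known but the number of seizures is unknown, the number of seizures will be imputed using the median" for that type. SAP 8.3.2.22 has no rule for a Maintenance day on which the diary is missing altogether.

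**The concern.** The two sides of the comparison treat missing days differently. The target is a rate per observed day scaled to 28 days. The quantity that has to reach it is a raw running total, read against the calendar. A missing Maintenance day moves the clock forward but cannot add a seizure, so it has the same effect as a recorded seizure-free day. The SAP does not say this in words; it follows from a cumulative count on a calendar clock with no missing-day rule.

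Two things are at stake. The first is the 28-day benchmark, which is the SAP's stated way of reading the result: a subject with an unchanged seizure rate and a gappy diary passes 28 days and is read as improved. The second is the log-rank comparison, which would be distorted if one arm kept poorer diaries than the other.

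**Working it through.** **Other rules that might close the gap**
- The non-missing-day denominator (SAP 4.2.1.1) applies to seizure frequency, not to a running count on a calendar clock.
- The count imputation in the same section needs a known seizure type. It does not reach a day with no entry.
- Censoring at the last non-missing day (SAP 8.3.2.22) removes a gap at the end of the record, not a gap before the event.
- Subjects with unacceptably incomplete diaries leave the PPS (SAP 4.2.1.1), but this analysis uses the FAS (SAP 8).
- By contrast, SAP 8.3.1.2 explicitly drops days without diary data when computing seizure-free days.

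**The SAP's own benchmark**

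Let c be the share of Maintenance diary days completed and r the ratio of the Maintenance to the Baseline seizure rate. Recorded seizures accrue at c × r times the Baseline daily rate, so

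expected calendar days to the Baseline count ≈ 28 / (c × r).

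With c = 1 and r = 1 this gives 28.0 days, the SAP's benchmark.

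**Unchanged rate (r = 1), incomplete diary**

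| c (assumed) | 28 / c | Apparent rate reduction, 1 − c |
|---|---|---|
| 100% | 28.0 days | 0% |
| 95% | 29.5 | 5% |
| 90% | 31.1 | 10% |
| 85% | 32.9 | 15% |
| 80% | 35.0 | 20% |
| 70% | 40.0 | 30% |

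An unchanged rate at 80% completion (28/0.80 = 35.0) cannot be told apart from a true 20% reduction with a complete diary (28/(1 × 0.80) = 35.0). The 80% level is the cut used for the compliance summary in SAP 7.2. It is not a forecast.

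**Between-arm comparison, by simulation**

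Inputs from the SAP: 80 subjects per arm (2.7), a 12-week (84-day) Maintenance Period, and a log-rank test at nominal two-sided 0.05 (8.3.2). Assumptions: no difference between arms and an unchanged rate; median about 10 seizures per 28 days with log-SD 0.9 and at least 4 at Baseline; overdispersed daily counts; complete Baseline diary; Maintenance days missing at random. There were 400 runs per scenario, so the simulation error at 5% is √(0.05 × 0.95 / 400) ≈ 1.1 percentage points.

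| Completion, placebo vs PSL | Calendar clock: rejected | Calendar medians (days) | Diary-day clock: rejected | Diary-day medians |
|---|---|---|---|---|
| 100% vs 100% | 5.0% | 29 vs 29 | 5.0% | 29 vs 29 |
| 95% vs 95% | 7.5% | 30 vs 30 | 6.5% | 29 vs 29 |
| 95% vs 90% | 9.8% | 30 vs 32 | 5.0% | 29 vs 29 |
| 95% vs 85% | 30.2% | 30 vs 34 | 4.2% | 29 vs 29 |
| 95% vs 80% | 54.0% | 31 vs 36 | 7.0% | 29 vs 29 |
| 80% vs 80% | 4.0% | 36 vs 36 | 5.0% | 29 vs 29 |

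Where completion was unequal, essentially every rejection on the calendar clock favoured the arm with the poorer diary. With equal completion of 80% the test held its level, but both medians moved from 29 to 36 days.

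The result at 95% versus 85% depends on the assumed seizure rates. Four other rate distributions (200 runs each) gave 24–38%. At 95% versus 92% they gave 5–9.5%, close to nominal.

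**The case against.** The strongest reply is that little depends on this. The variable is one of many other efficacy variables, tested at nominal 0.05 without multiplicity adjustment (SAP 8.3.2). It lies outside the Hochberg testing of the primary variables (SAP 4.5). The primary and secondary variables are built on frequencies with a non-missing-day denominator. All of this stands and sets the severity.

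The plan also limits diary gaps. Entries are reviewed at each visit, caregivers may help, and incomplete diaries can lead to discontinuation (Protocol 7.7 and 9.1). Compliance is summarised by arm for the Maintenance Period (SAP 7.2), so an imbalance would be visible. These measures make large gaps less likely, but none corrects a gap once it is there.

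The Baseline scaling is not only a missing-data correction. Visit 2 falls 4 to 5 weeks after Visit 1 (Protocol 8.2.1.1), so some rescaling to 28 days is needed even with a complete diary. That is true, but it does not supply the correction missing on the Maintenance side.

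A reader might infer that the log-rank test is biased towards padsevonil, for instance through dose-related somnolence or fatigue. The documents give no completion figures and do not link diary gaps to dose. The bias needs unequal completion and could favour either arm. A reader might also infer that every arm's median is too long, or that this is the only seizure variable without a non-missing-day denominator. The first holds only where days are missing before the event. The second is wrong: seizure freedom (SAP 8.3.1.1) instead requires that no diary day be missing.

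**Conclusion.** The point holds, as a minor one. As written, SAP 8.3.2.22 gives a wrong reading whenever a Maintenance diary day is wholly missing before the event. The expected time at an unchanged rate is then about 28/c rather than 28 days, so a time over 28 days does not by itself show reduced seizure frequency. This is arithmetic. It does not depend on the simulation or on any difference between arms; it assumes only that the rate on missing days is the same as on recorded days.

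The between-arm effect is conditional. It is large at an assumed 10-point difference in completion (about 24–38% rejection with no drug effect) and near nominal when completion is equal or nearly so. Completion levels and seizure-rate distributions are assumptions, because the documents give neither. Nothing here touches the primary or secondary conclusions.

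**What to change.** In SAP 8.3.2.22:
- Define time to event as the number of non-missing Maintenance diary days up to and including the event day.
- Censor subjects who do not reach the target at their total number of non-missing Maintenance diary days. The existing Day 1 censoring for subjects who discontinue during Titration and Stabilization can stay.
- Amend the time formula and the 28-day interpretation sentence, so that the benchmark reads as 28 completed diary days.
- Keep the calendar-day version as a sensitivity analysis, so that results stay comparable with the published endpoint the section cites.

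Like SAP 4.2.1.1 for frequencies, this assumes that missing days resemble recorded ones. In the simulations above, the diary-day clock kept the median at 29 days and rejection at about 4–7%.

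The cost is a few sentences in one section and one derived variable. No new data are needed, because SAP 7.2 already identifies missing diary days.

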### **8.3.2.23 Change from baseline in seizure frequency**

The 28-day adjusted seizure frequency and change from baseline will be summarized descriptively by the treatment group in Titration and Stabilization, Maintenance, and Treatment Periods for observable focal-onset seizures and Type I seizures. The imputation rule described in Section 4.2.1 will be applied.

### **8.3.2.24 Additional figures for efficacy variables**

The following figures will be generated using the FAS: median percent reduction in seizure frequency, 75% RR, and 50% RR in observable focal-onset seizures will be displayed for the 16-week Treatment Period and the 12-week Maintenance Period by treatment group.

### **8.3.2.25 Use of health-related outcomes and HRU**

Health-related outcomes data and HRU data will be listed for the RS and summarized descriptively for the SS. Hospital and ER Visits will be listed for SS.

- Socio-professional status

Socio-professional status data are collected at Visit 1 and Visit 7/EDV. Variables include highest level of education, housing status, current professional status, current unemployed status, need for regular assistance due to epilepsy, and ability to drive. The number and percentages of subjects in each category will be summarized for Visit 1, Visit 7, and the Last Visit during the Treatment Period.

- Healthcare provider consultations not foreseen by the protocol

The number of health care provider consultations per subject with onset during the Treatment Period will be summarized as a continuous variable as well as in the following categories: 0, 1, 2, 3, 4, and 5 or more. Additionally, the number and percentage of consultations by type of provider (general practitioner, specialist physician, nurse, and other) will be presented for the Treatment Period.

- Hospital and ER visits

The number of hospitalizations per subject will be summarized as a continuous variable and categorical variable for the Treatment Period. ER visits will be extracted from the Hospitalization/ER Visit CRF page (if the initial entry point is ER). The number of ER visits will be summarized in the same manner as hospitalizations. Additionally, the number and percentage of subjects with each of the following categories of duration of hospital stay will be summarized: 0 days, 1-5 days, 6-10 days, 11-15 days, and >15 days.

- Caregiver assistance

Caregiver assistance data is collected on the CRFs “Caregiver Assistance Screening” and “Caregiver Assistance Follow-up”. The number and percentages of subjects having a caregiver will be summarized by visit.

- Concomitant medical procedures

The number of concomitant medical procedures per subject during the Treatment Period will be summarized using the categories 0, 1, 2, and 3 or more.

- Number of school or working days lost

Number of school/working days lost data are collected on the CRFs “School and Workdays Lost Screening” and “School and Workdays Lost Follow-up”. The number and percentages of subjects who lose school or work days as a result of epilepsy will be summarized by visit.

The percentage of days lost will be summarized by visit for subjects who have more than zero total number of school or work days. The percentage of days lost will be calculated as:

$100 \times (\text{end date of absence} - \text{start date of absence} + 1) / (3 \times 30 + 1)$  for the screening visit. If the end date of absence is missing or after Visit 1 date, the end date of absence will be set to Visit 1; if the start date of absence is missing or prior to Visit 1-90, the start date of absence will be set to Visit 1-90.

$100 \times (\text{end date of absence} - \text{start date of absence} + 1) / (\text{visit date of current visit} - \text{visit date of previous visit} + 1)$  for the later visits. If the end date of absence is missing or after the current visit date, the end date of absence will be set to the current visit date; if the start date of absence is missing or prior to the previous visit+1, the start date of absence will be set to the previous visit date+1.

If multiple absences are reported at a given visit, the sum of the duration of all absences will be used in the numerator.

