3.3 Other objectives

3.3.1 Efficacy objectives

The other efficacy objective is to:

- Assess the HRU and quality of life

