### **3.2.2.2 End of the 16-week treatment period**

The end of the 16-week overall treatment period will be either the date of Visit 7 for subjects completing the Treatment Period, or the date of the early discontinuation visit (EDV), for subjects who discontinued during the Treatment Period. If a subject does not have a Visit 7/EDV, then the date of the final contact will define the end date of the Treatment Period.

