**Table 3–1: Start and end of EP0091 analysis periods**

Analysis Period			Details
Description	Start	End	
Baseline (Week -4)	Date of informed consent at Visit 1	Date of the day before the date of Visit 2.	This is an approximate 28-day period for calculation of Baseline seizure frequencies. Study drug is dispensed, and first dose is generally taken the day of the Baseline Visit (Visit 2, Day 1). Note the pre-dose assessments will also be included in the Baseline Period.
Titration and Stabilization*	The date of the Baseline Visit, (Visit 2, Day 1).	The date of the day before Visit 4 or the end of the treatment period if the subject has discontinued prior to Visit 4.	For evaluation purposes, if results are presented by analysis period, the Titration and the Stabilization interval will be considered together (approximately 4 weeks in total). Titration is a period of dose increases to reach the protocol specified dose. Stabilization is an approximate week-long interval to stabilize at the target dose level. During stabilization the dose may be adjusted once (i.e. to a fallback dose).
Maintenance*	The date of Visit 4.	The date of Visit 7 or the end of the treatment period if the subject has discontinued prior to Visit 7.	This is a 12-week period where the subject remains on the randomized target dose (or fallback dose, if applicable).
16-week Treatment Period*	The date of the Baseline visit (Visit 2)	The date of Visit 7 or the end of the treatment period if the subject has discontinued prior to Visit 7.	Titration and Stabilization Period and Maintenance Period combined.
Conversion	The date of the day after Visit 7	The date of Visit 8.	This is a 3-week period of dose conversion to enable the subjects to enroll into the OLE study EP0093.
Taper and Safety Follow-up	The date of the day after Visit 7/EDV or the date of day after Visit 8 if the subject tapered after conversion	The date of final contact.	Subjects who withdraw from the study or decide not to participate in the OLE study will be tapered off the IMP during a 3-week period followed by a 1-week drug-free period. A SFU visit will be performed 30 days after the last IMP intake.

OLE=open-label extension; SFU=Safety Follow Up

\* Only seizure data prior to and on the date of last dose of study medication will be included in the analysis.

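### Four healthcare-use counts in SAP 8.3.2.25 take no account of observation time, so if dropout differs between arms they mix event rate with length of follow-up

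*SAP*

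**What the plan says.** Protocol 3.3.1 names one other efficacy objective: "Assess the HRU and quality of life". SAP 8.3.2.25 sets out the healthcare resource utilisation (HRU) summaries and the analysis set: "Health-related outcomes data and HRU data will be listed for the RS and summarized descriptively for the SS". The Safety Set includes every dosed subject, early leavers among them.

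Four items are event counts:
- Consultations: "The number of health care provider consultations per subject with onset during the Treatment Period will be summarized as a continuous variable", and also in categories from 0 to 5 or more.
- Hospitalisations: "The number of hospitalizations per subject will be summarized as a continuous variable and categorical variable for the Treatment Period".
- ER visits: handled in the same way as hospitalisations.
- Concomitant procedures: "The number of concomitant medical procedures per subject during the Treatment Period will be summarized", in categories only.

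The counting window closes early for discontinuers. SAP 3.2.2.2 ends the 16-week period at Visit 7 for completers "or the date of the early discontinuation visit (EDV), for subjects who discontinued during the Treatment Period", or at final contact if neither visit took place. Table 3-1 agrees: "The date of Visit 7 or the end of the treatment period if the subject has discontinued prior to Visit 7". SAP 8.3.2.25 gives no rate, offset, person-time denominator or completer restriction for these four items. SAP section 8 presents efficacy tables by treatment group.

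**The concern.** A subject who leaves at week 3 is watched for 3 weeks and a completer for 16. Both enter the mean, and the 0, 1, 2 categories, as one subject. If one arm loses more subjects than another, its mean count falls and its zero category grows, even when the drug has no effect on use of care. A reader comparing the columns cannot tell fewer events per week from fewer weeks.

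Elsewhere the SAP does adjust for observation time. Seizure counts are scaled to 28 days (SAP 3.3.1, 8.1.1.1). Seizure-free days are divided by available diary days (SAP 8.3.1.2). School or work days lost, in the HRU section itself, are a percentage of the interval between visits. The four event counts are the exception.

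Unequal dropout is possible. Protocol 5.1 withdraws subjects who cannot tolerate treatment before Week 3. Protocol 6.3 lists seizure worsening and psychiatric disturbance among its withdrawal criteria. At stake is the reading of a descriptive summary tied to a stated objective.

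**Working it through.** **Inputs.** The full window is 16 weeks, or 112 days (SAP 3.2.2.2, Table 3-1). The planned arm size is 80 (SAP 2.7). The plan has no HRU or dropout figure to reproduce; its only attrition figure is the 20% screening failure rate, which applies before randomisation. The dropout share d and the mean exit week w are therefore assumptions, shown over a range.

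**Step 1: observed time, equal rates.** Mean observed weeks = (1 - d) x 16 + d x w. If the event rate is constant and the same in both arms, the ratio of mean counts equals the ratio of mean observed weeks.

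| Dropout, lower v higher | Mean exit week | Mean observed weeks | Ratio of counts |
|---|---|---|---|
| 10% v 20% | 8 | 15.2 v 14.4 | 0.95 |
| 10% v 20% | 4 | 14.8 v 13.6 | 0.92 |
| 10% v 30% | 8 | 15.2 v 13.6 | 0.89 |
| 10% v 30% | 4 | 14.8 v 12.4 | 0.84 |
| 10% v 10% | 4 or 8 | equal | 1.00 |

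For example, 0.90 x 16 + 0.10 x 4 = 14.8, 0.70 x 16 + 0.30 x 4 = 12.4, and 12.4 / 14.8 = 0.84. The spurious shortfall is 5-16%. A more extreme 5% v 35% split gives 15.4 v 11.8 weeks at exit week 4 (23% fewer) and 15.6 v 13.2 at week 8 (15% fewer).

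**Step 2: the zero category.** Assume one consultation expected per 16 weeks, Poisson, with exit at week 4. The share with none is (1 - d) x exp(-1) + d x exp(-0.25). That is 40.9% at d = 0.10 and 49.1% at d = 0.30, with no drug effect.

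**Step 3: the same data as a rate.** Take 80 per arm, 10% v 30% dropout, exit at week 4, and one event per 16 weeks.
- Expected events: 80 x 14.8/16 = 74 and 80 x 12.4/16 = 62.
- Subject-days: 80 x 14.8 x 7 = 8,288 and 80 x 12.4 x 7 = 6,944.
- Events per 28 subject-days: 74 x 28 / 8,288 = 0.25 and 62 x 28 / 6,944 = 0.25, so the ratio is 1.00.

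**Step 4: leavers who use more care before exit.** If leavers use care at r times the completers' rate while observed, the relative mean count is (1 - d) + d x r x w/16. With 10% v 30% dropout and w = 4, the ratio of counts is 0.84 at r = 1, 0.89 at r = 2, 1.00 at r = 4 and 1.10 at r = 6. The break-even is r = 16/w.

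**Step 5: what the rate does not fix.** At r = 4 in the same scenario, raw counts are equal, but the rate in the arm with more dropout is 8,288 / 6,944 = 1.19 times the other, because its heavier users contributed little time. Dividing by person-time corrects for unequal observation; it does not remove informative dropout.

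**The case against.** The strongest reply is that little depends on these tables. HRU is in the list of other efficacy variables, summarised descriptively, with no test or model. Tolerability is read from adverse events leading to discontinuation (SAP 10.2). With 80 per arm and one event expected per subject, the 95% interval on a log rate ratio is about ±1.96 x sqrt(2/80) = ±0.31, wider than a 5-16% artefact. All of this stands and limits the importance of the point.

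Second, SAP 10.1 already tabulates Treatment Period exposure in days for the Safety Set. A reader could divide mean count by mean days and multiply by 28. This works approximately for consultations, hospitalisations and ER visits, and differs where the last dose precedes the discontinuation visit. It does not work for procedures, which appear only in categories.

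Four stronger readings are tempting, but the documents do not support them:
- **Dropout will rise with dose.** No dropout rate by arm or dose is given. Protocol 2.3.1 reports 18 EP0069 subjects with adverse events leading to dose reduction, but only one who withdrew for adverse events, and EP0069 titrated to a single target dose. It cannot show a dose gradient in dropout. Withdrawal for seizure worsening could fall on placebo.
- **More dropout always means a lower count.** Step 4 shows that this depends on how heavily leavers use care before they exit.
- **All HRU is unadjusted.** Days lost are a percentage of the visit interval, and caregiver use is a percentage by visit.
- **Care after discontinuation is lost.** HRU is recorded at Visits 8 and 9 (Protocol Table 5-1) and listed for the Randomized Set. It is missing from the Treatment Period summaries, not from the report.

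**Conclusion.** The point holds in conditional form. For consultations, hospitalisations, ER visits and procedures, the planned per-subject counts confound event rate with observation time whenever dropout differs between arms. With equal, constant rates, 10% v 20-30% dropout and mean exit at week 4 to 8, the arm with more dropout would show 5-16% fewer events. With equal dropout there is no distortion. The size rests wholly on assumed dropout, and the direction rests on leavers using care at a broadly similar rate while observed. With exit at week 4, the effect disappears at four times the completers' rate and reverses above that. No hypothesis test, error rate or primary conclusion is affected. This is a cheap improvement to descriptive tables, not a flaw in the trial.

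**What to change.** In SAP 8.3.2.25, for consultations, hospitalisations, ER visits and concomitant procedures, add by treatment group:
- total events in the Treatment Period;
- total Treatment Period subject-days, using the end date in SAP 3.2.2.2;
- events per 28 subject-days (total events / total subject-days x 28).

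Keep the per-subject counts and categories alongside. Summarise HRU recorded at Visits 8 and 9 separately for subjects who taper, because the rate does not deal with informative dropout. Add a note that the rate is to be read with the discontinuation tables in SAP 5.1.

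The cost is SAP wording, one extra line per table and a short additional summary for tapering subjects. All the data are already collected. The downside is slightly longer tables and a rate that needs the discontinuation pattern beside it to be interpreted.

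### After Screening, the percentage of school or work days lost is divided by one day more than the absence rule can count, so non-zero values come out slightly low

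*SAP*

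**What the plan says.** SAP 8.3.2.25 gives two formulas for the percentage of school or work days lost, and the results are summarized by visit. Both count an absence inclusively, as end date minus start date plus 1.

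- **Screening.** The denominator is 3 × 30 + 1. The limits are: "if the start date of absence is missing or prior to Visit 1-90, the start date of absence will be set to Visit 1-90", and "If the end date of absence is missing or after Visit 1 date, the end date of absence will be set to Visit 1".
- **Later visits.** The denominator is current visit date minus previous visit date, plus 1. A missing start, or one before the day after the previous visit, is moved: "the start date of absence will be set to the previous visit date+1". For a missing or later end, "the end date of absence will be set to the current visit date".
- **Several absences.** "If multiple absences are reported at a given visit, the sum of the duration of all absences will be used in the numerator". There is no rule for overlapping records.

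Protocol Table 5-1 schedules the health-related outcomes and HRU record at Visits 1 to 9. Protocol 8.2.1.1 includes it at Visit 2 and leaves out only socio-professional status there.

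**The concern.** A percentage of days lost should use the same window above and below the line. After Screening it does not. The previous visit day is in the denominator, but the rule for start dates keeps it out of the numerator. An absence that begins on the previous visit day is also moved forward, so no reading of the rule brings that day back.

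The shortfall depends on the gap between visits. A constant level of absence therefore gives different percentages at visits with different gaps, and a different percentage at Screening. Because the table is by visit, these movements would appear in adjacent rows and could be taken for real change.

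**Working it through.** **Inputs.** The formulas and limits are those of SAP 8.3.2.25. The visit gaps come from the protocol: Visit 2 is 4 to 5 weeks after Visit 1 (8.2.1.1), Visit 3 is at Week 2 ± 1 week (8.2.1.3), and Visits 4, 5, 6 and 7 are at Weeks 4, 8, 12 and 16 (8.2.3). The nominal gaps are then 28 days to Visit 2, 14 days to each of Visits 3 and 4, and 28 days to each of Visits 5, 6 and 7.

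**Screening, the SAP's own figure.** The longest countable absence is V1 − (V1 − 90) + 1 = 91 days. The denominator is 3 × 30 + 1 = 91. The maximum is 91/91 = 100%, so the two windows agree.

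**Later visits.** Let p be the previous visit date, c the current visit date and D = c − p.

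- Longest countable absence: c − (p + 1) + 1 = D.
- Denominator: c − p + 1 = D + 1.
- Maximum: D/(D + 1), always below 100%.

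An enumeration of all single-absence start and end dates for D = 1 to 59 gave this maximum every time. Splitting one absence into two non-overlapping records over a 28-day gap gave 28/29 again.

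**Continuously absent subject**

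| Visit | Gap D (days) | Percentage | Below Screening (points) |
|---|---|---|---|
| Screening | – | 91/91 = 100% | – |
| 2 | 28 | 28/29 = 96.55% | 3.45 |
| 3 | 14 | 14/15 = 93.33% | 6.67 |
| 4 | 14 | 14/15 = 93.33% | 6.67 |
| 5, 6, 7 | 28 | 28/29 = 96.55% | 3.45 |

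At the edges of the visit windows the value is 7/8 = 87.5% for a 7-day gap (Visit 3 one week early) and 35/36 = 97.2% for a 35-day gap (Visit 2 at 5 weeks). No two consecutive visits are nominally 7 days apart.

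**Shorter absences.** An absence of n days gives n/(D + 1) instead of n/D. The ratio is D/(D + 1), so the relative shortfall is 1/(D + 1) whatever n is.

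- 1 day in 28: 1/29 = 3.45% instead of 1/28 = 3.57%, a shortfall of 0.12 points.
- 3 days in 28: 3/29 = 10.3% instead of 3/28 = 10.7%, a shortfall of 0.4 points.
- 3 days in 14: 3/15 = 20.0% instead of 3/14 = 21.4%, a shortfall of 1.4 points.

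**The case against.** The case against making much of this is strong on consequences, though not on the arithmetic.

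- **Improvement on treatment.** A reader might infer that an always-absent subject appears to improve once treated. The documents do not support that. Visit 2 is recorded before dosing and already uses the later-visit formula. SAP 3.3.2 takes the last valid measurement before the first dose as Baseline for non-seizure variables. At nominal spacing Visit 2 has the same 28-day gap and the same 96.6% ceiling as Visits 5 to 7, so constant absence shows no change between them. The step from 100% to 96.6% happens before treatment.
- **Visit 3 as the low point.** A reader might take Visit 3 as the worst case. Visits 3 and 4 both follow a nominal 14-day gap and share the 93.3% ceiling. Against Visit 2 the dip is 96.55 − 93.33 = 3.22 points at each.
- **Never 100%.** This holds only for non-overlapping absences. Durations are summed without an overlap rule, so a full 28-day record plus an overlapping 9-day record gives 37/29 = 127.6%. That is a separate gap and does not repair the formula.
- **Bias between arms.** The formula and schedule are the same in every arm. At equal visit spacing neither padsevonil nor placebo is favored. HRU data are summarized descriptively, and no test or change from Screening is specified for this percentage.
- **Comparability with Screening.** Screening has its own CRF page and a 91-day look-back, against nominal gaps of 14 or 28 days through Visit 7. Correcting the denominator does not make the two fully comparable.

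All five points stand. They limit how much the error matters, but the denominator still does not match the window.

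**Conclusion.** The later-visit formula is wrong as written, and the error is minor. For non-overlapping absences every non-zero percentage after Screening is too low by 1/(D + 1) in relative terms: 1/29 = 3.4% for a 28-day gap and 1/15 = 6.7% for a 14-day gap. The point differences in the table above are the upper limit at nominal spacing, because they apply to a subject absent every calendar day. The documents do not say how many such subjects to expect, and for short absences the loss is mostly a fraction of a point.

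What a reader of the table would see is a small artificial step from Screening to Visit 2 and a dip at Visits 3 and 4. The sizes assume nominal visit spacing, and actual gaps will move them within the range shown. No primary or secondary efficacy result is affected.

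**What to change.** In SAP 8.3.2.25, for later visits, divide by the current visit date minus the previous visit date. That is the number of days from the day after the previous visit to the current visit. A continuously absent subject then scores 28/28 or 14/14, which is 100% at every visit, and successive windows do not overlap.

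Keeping the denominator and moving the earliest start back to the previous visit date would also reach 100%, but each visit day would then fall in two adjacent windows. The first option is cleaner.

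The cost is one + 1 deleted from the SAP formula and from its program. No new data are needed, and the Screening formula stays as it is.
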